### 8.5 Adverse events, SUSARS, and serious adverse events

An **adverse event** (AE) is defined as any untoward medical occurrence in a patient or clinical investigation subject administered a pharmaceutical product at any dose that does not necessarily have to have a causal relationship with this treatment. An AE can, therefore be any unfavourable and unintended sign (including an abnormal laboratory finding, for example), symptom, or disease temporally associated with the use of an investigational product, whether or not considered related to the investigational product. This definition includes intercurrent illnesses or injuries and exacerbation of pre-existing conditions.

All AEs will be monitored until resolution or, if the AE becomes chronic, a cause identified. If an AE is unresolved at the conclusion of the study, a clinical assessment will be made by the investigator and Medical Monitor whether continued follow-up of the AE is warranted

The severity of events reported on the Adverse Events CRF will be determined by the investigator as:

- **Mild:** Transient effect with no limitation in normal daily activity.
- **Moderate:** Some limitation in normal daily activity, but no medical attention needed.
- **Severe:** Unable to perform normal daily activity and requiring medical attention.

The relationship of the study treatment to an AE will be determined by the investigator based on the following definitions:

- **Not Related:** The AE is not related if exposure to the investigational vaccine has not occurred, **or** the occurrence of the AE is not reasonably related in time, **or** the AE is considered unlikely to be related to use of the investigational vaccine, i.e. there are no facts (evidence) or arguments to suggest a causal relationship.
- **Possibly Related:** The administration of the investigational vaccine and AE are considered reasonably related in time **and** the AE could be explained by causes other than exposure to the investigational vaccine
- **Probably Related:** Exposure to the investigational vaccine and AE are reasonably related in time **and** the investigational vaccine is more likely than other causes to be responsible for the AE, **or** is the most likely cause of the AE.

The relationship of the study treatment to an AE will be determined by the Principal Investigator.

A **suspected unexpected serious adverse event** (SUSAR) is one that is not listed in the current Summary of Product Characteristics or the Investigator's Brochure or an event that is by nature more specific or more severe than a listed event.

A **serious adverse event** (SAE) is defined as any untoward medical occurrence that at any dose:

- Results in death;

- Is life-threatening (i.e., the subject was, in the opinion of the investigator, at immediate risk of death from the event as it occurred); it does not refer to an event which hypothetically might have caused death if it were more severe;
- Requires or prolongs inpatient hospitalization;
- Results in persistent or significant disability/incapacity (i.e., the event causes a substantial disruption of a person's ability to conduct normal life functions);
- Results in a congenital anomaly/birth defect;
- Requires intervention to prevent permanent impairment or damage;
- Is an important and significant medical event that may not be immediately life threatening or resulting in death or hospitalization but, based upon appropriate medical judgment, may jeopardize the patient/subject or may require intervention to prevent one of the other outcomes listed above.

Of note: a "possible vaccine failure" should be reported as a serious AE only if it resulted in an infectious disease which should have been prevented by the vaccine implied.

Adverse events which do not fall into these categories are defined as **non-serious**. It should be noted that a severe adverse event need not be serious in nature and that a serious adverse event need not, by definition, be severe.

In addition, a pre-existing event or condition that results in hospitalization should be recorded on the medical history CRF. If the onset of an event occurred before the subject entered the trial (e.g., any pre-planned hospitalization for conditions like cosmetic treatments or for non-emergency routine visits for a pre-existing condition), the hospitalization would not lead to an AE being classified as serious unless, in the view of the investigator, hospitalization was prolonged as a result of participation in the clinical trial or was necessary due to a worsening of the pre-existing condition

## **8.6 Documentation/reporting of adverse and other clinical events**

All study subjects will be observed for at least 30 minutes after a vaccination for evidence of immediate reactions in general and in particular for symptoms of allergic phenomena (such as rashes, itching, or other allergic manifestations). Each subject, or where applicable, the subject's legally acceptable representative(s) will be instructed to complete a diary card for 7 days following each administration, to describe local and systemic reactions and other selected indicators of reactogenicity. If a local and systemic reaction or fever (derived from measured oral temperatures  $\geq 38.0^{\circ}\text{C}$ ) continues beyond the 7-day period after a vaccination, it will also be recorded on the Adverse Events CRF. If the subject recovers on the last day, then this fact will be recorded on the Local and Systemic Reaction CRF. All AEs must be reported and documented. The period of observation for adverse events extends from the time the subject receives vaccination through until 3 weeks after vaccination.

All AEs necessitating a physician's visit or consultation and/or leading to premature study discontinuation and all SAEs will be collected throughout the entire study and data will be reconciled at study termination.

All adverse events, regardless of severity, will be monitored by the investigator until resolution. All subjects experiencing adverse events - whether considered associated with the use of the study

vaccine or not - must be monitored until symptoms subside and any abnormal laboratory values have returned to baseline, or until there is a satisfactory explanation for the changes observed, or until death, in which case a full pathologist's report should be supplied, if possible. All findings must be reported on an Adverse Events CRF and on the "Serious Adverse Event" form, if necessary, which is part of the investigator's study file. All findings in subjects experiencing adverse events must be reported also in the subject's medical records.

In addition, any event resulting in a subject's withdrawal from subsequent vaccinations or from follow-up should be reported according to the protocol instructions.

All SAEs which occur during the course of the trial, whether considered to be associated with the study vaccination or not, have to be reported **within 24 hours** by telephone or fax to either of the following:

### **Post-Study Events**

Any AE occurring at any time outside the observation period or after the end of the study and considered to be caused by the study vaccine - and therefore a possible adverse drug reaction - must be reported to the sponsor.

#### **Halting criteria**

Any serious adverse reaction will be reported to the sponsor and EC in accordance with the European Directive 2001/20/EC. If any serious adverse event is considered as probably related to the study vaccine, this will be considered by the Chief Investigator, study co-applicants, sponsor, and DH representatives who will make a collective decision to continue or halt the study.

### **8.7 Study monitoring/auditing**

Investigators and/or their study staff will be trained at the latest during the initiation meeting. Monitoring and auditing procedures will be followed in order to comply with GCP guidelines and to ensure validity of the study data. During each monitoring visit source data verification will be performed by qualified staff.

#### **8.7.1 Monitoring**

The clinical study sites will be monitored by regular site visits and telephone calls to the investigator by qualified staff representing the Sponsor. By frequent communication, the site monitor will ensure that the study is conducted according to the protocol. CRFs and all original data collected at the site should be available for review during monitoring visits. During these visits, the site monitor should review drug accountability records and might review document retention including the Investigator's Study File. Additionally, the site monitor should check that clinical study procedures are observed and discuss any problems with the investigators.

#### **8.7.2 Source data verification**

Inspection and examination of CRFs and source documents (all original recordings, medical records) - giving due consideration to data protection and medical confidentiality - will be undertaken by representatives of the Sponsor.

All data not recorded directly on the CRFs as defined in section 8.7.3 of this study protocol will be verified by checking CRF entries against source documents in order to ensure that the data have been completely and accurately reported as required by the study protocol.

Source data verification will be performed and recorded following the sponsor's SOP. The subject or the subject's legally acceptable representative must also allow access to the subject's medical records, if required. Each subject, or the subject's legally acceptable representative, will be informed of this prior to the start of the study.

During or after the clinical study, the regulatory authorities, the EC and/or representatives of the sponsor may request access to all source documents, CRFs and other study documentation for on-site audit or inspection.

#### **8.7.3 Documentation of study findings**

All study data must be entered into the CRFs by the investigator who will sign and date the entries. If the investigator authorizes other persons in his/her staff to make entries on the CRF, the names, positions, signatures, and initials must be supplied to the sponsor.

The following data may be reported directly on the CRFs and are considered to be source data:

- Medical history,
- Vaccination time, Concomitant medication,
- Study termination, and
- Comments.

CRFs must be completed during/after each study visit.

A reasonable explanation must be given by the investigator for all missing data.

If corrections are made to entries in the CRF by the investigator or designates, the words or figures must be crossed through, leaving the initial entry legible. The correction must then be dated and initialed. Incorrect entries must not be covered with correcting fluid, obliterated, or made illegible in any way. If further corrections are made after review and signature by the investigator, he/she must confirm and endorse the changes by signing and dating the study termination CRF again.

As part of the conduct of the trial, the sponsor may have questions about the CRF data. These questions will be documented using Data Clarification Forms (DCFs). The investigator will file each of the DCFs for the trial.

### **8.8 Record retention**

Investigators must retain all study records according to applicable regulations in a secure and safe facility. The investigator must notify the sponsor of any change in the location, disposition, or custody of the study files.

Upon completion of the study, all study documents will be collated and stored by the Chief Investigator.

The Committee for Human Medicinal Products (CHMP) requires retention for the maximum period of time permitted by the institution, but not less than 15 years. It is the responsibility of the sponsor to inform the investigator/institution as to when these documents no longer need to be retained.

### **8.9 Data protection**

The sponsor respects the subjects' rights to privacy and will ensure the confidentiality of their medical information in accordance with all applicable laws and regulations. The sponsor as Data Controller according to the European Directive on the protection of individuals with regard to the processing of personal data and on the free movement of such data [95/46/EC] confirms herewith compliance to Directive 95/46/EC in all stages of Data Management.

### **8.10 Changes in the conduct of the study or planned analysis**

Planned changes in the conduct of the study will be described in protocol amendments; changes in the planned analysis will be described in the clinical study report. An amendment is a written description of change(s) to, or formal clarification of, a study protocol. The EC must be informed of all amendments and if necessary prior review and documented approval/favourable opinion must be sought for ethical aspects. Approval must also be obtained from the authorities, if necessary. Such amendment will be agreed upon by the sponsor, the investigator, the EC and authorities, if necessary, prior to implementation.

## **9.0 ANALYSIS**

### **9.1 Blood sampling windows**

Blood samples taken in the following time windows will be evaluable:

- Pre-immunization: Day 0
- Post-immunization: Day 7 (window: Day 6–Day 8)  
Day 14 (window: Day 12–Day 16)  
Day 21 (window: Day 19–Day 23)  
Day 28 (window; Day 26–Day 30)  
Day 35 (window: Day 32–Day 38)  
Day 42 (window: Day 39–Day 45)  
Day 180 (window: Day 170–Day 190)

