### 1.2 Definition of terms

**Adverse Event:** An Adverse Event (AE) is any untoward medical occurrence in a patient or clinical investigation subject administered a pharmaceutical product at any dose that does not necessarily have to have a causal relationship with this treatment. An AE can, therefore be any unfavourable and unintended sign (including an abnormal laboratory finding, for example), symptom, or disease temporally associated with the use of an investigational product, whether or not considered related

to the investigational product. This definition includes intercurrent illnesses or injuries and exacerbations of pre-existing conditions.

**Concomitant medication:** All prescription medication, being taken by the subjects on entry to the study and all prescription medication given in addition to the study vaccine during 21 days after each vaccination are to be regarded as concomitant medication

**End of Trial:** The End of Trial corresponds to the last visit of the last subject undergoing the trial (LSLV, Last Subject Last Visit).

**Local and Systemic Reactions:** Selected local and systemic AEs are routinely monitored in vaccine clinical trials as indicators of vaccine reactogenicity. It is recognized that each of these events, and particularly those of a systemic nature, may under some circumstances, in any individual subject, have a cause that is unrelated to the study vaccine. However, as a matter of convenience and in accordance with common clinical practice, all such events occurring within 6 days after immunization are herein termed 'local and systemic reactions'.

**Month, Day:** Study months are based upon 30-day cycles. The study day refers to the number of days after enrollment, with the day of first vaccination being designated day 0.

**Serious Adverse Event:** Any experience or reaction that suggests a significant hazard, contraindication, side effect, or precaution. These events include any experience that is fatal or life-threatening, requires or prolongs inpatient hospitalization, is permanently disabling, leads to congenital abnormality, requires intervention to prevent permanent impairment or damage, or is important and significant medical event that, based upon appropriate medical judgment, may jeopardize the subject.

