#### TIME AND EVENTS TABLE

Study visit	1	2	3	4	5	6	7	8
	Days after the first vaccination							
Window (days)	0	( $\pm 1$ )	( $\pm 2$ )	( $\pm 2$ )	( $\pm 2$ )	( $\pm 3$ )	( $\pm 3$ )	( $\pm 10$ )
Study day	0	7	14	21	28	35	42	180
Informed consent	X							
Inclusion/exclusion criteria	X			X				
Medical/medication history	X							
Pregnancy test	X			X				
Blood sample – antibody studies	X	X	X	X	X	X	X	X
Vaccination	X			X				
Thermometer/Diary card	X			X				
Diary card training	X							
Diary card returned/review		X			X			
Reminder re unsolicited events	X	X	X	X	X	X	X	
Adverse events monitoring		X	X	X	X	X	X	X
Termination of study								X

Immunogenicity to influenza viruses will be evaluated by HI, MN, and possibly SRH responses.

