**Visit 4: Day 21 (+2): Second vaccination**

The following activities will be carried out on day 21 and recorded in the CRF:

1. Collect 10ml clotted blood for serology. Process blood and store serum.
2. For females of childbearing potential, perform a urine pregnancy test.
3. Check if the subject has taken an analgesic/antipyretic medication on Day 21 prior to study vaccination. Document this information on the subject's appropriate CRF.
4. Record oral temperature.
5. The vaccine administrator will give the same type of vaccine as before by IM injection in the deltoid muscle of the upper non-dominant arm.
6. Examine the site of injection of the vaccine for local reactions at the end of 30 minutes. These findings and any systemic reactions will be recorded on the appropriate CRF page.
7. Remind each subject in the evaluation of local and systemic reactions (e.g. how to measure the maximum diameter of induration and erythema in millimetres at the injection site and how to record temperature with a thermometer).
8. Give the second diary card. Tell subjects to:
  - Complete the diary at approximately the same time each day and to return it at the next visit;
  - Notify study personnel immediately if the subject experiences a SAE. Serious adverse events are defined in Sections 1.2 and 8.5.
  - Return the diary card to the site on the Day 28 visit.
9. Schedule the Day 28 visit.

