- Significant increase in antibody titre/area is defined as at least a fourfold increase in HI or a 50% increase in area from non-negative pre-vaccination serum ( $\geq 10$  for HI,  $\geq 4$  for SRH).

**Seroprotection:** Percentages of subjects achieving each of the following thresholds: inverse HI titre  $\geq 40$ , SRH area  $\geq 25 \text{ mm}^2$ : The number and proportion of subjects achieving each threshold at each visit will be tabulated for each vaccine/age group and each vaccine type.

All statistical analyses for HI and SRH will be performed on the logarithmically (base 10) transformed values. Titres below the limit of detection for assays will be set to 1 in 5 for HI and  $4 \text{ mm}^2$  for SRH for the purposes of analysis. Original values will be presented in all listings

The above immunogenicity criteria will be applied to sera collected 21 days after completion of vaccination, i.e., 21 days after the second vaccine dose. For pandemic vaccines, all three criteria should be met.

Should both GSK and Baxter vaccines satisfy all three CPMP criteria, we will compare the immunogenicity of the two vaccines (for each vaccine/age group and each vaccine type) in terms of:

- a. Geometric mean titres 21 days after each vaccination;
- b. Geometric mean ratio increases 21 days after each vaccination;
- c. Seroprotection rates 21 days after each vaccination;
- d. Seroconversion rates 21 days after each vaccination.

Comparisons will be made using parametric or non-parametric tests as appropriate for continuous outcomes, and Pearson's chi-square test or Fisher's exact test where appropriate for categorical outcomes. Further analyses using (generalised) linear models will explore the effect of baseline covariates on the outcomes. For populations (a) and (b), analyses using multiple imputation to allow for missing data will also be undertaken as a sensitivity analysis. No formal adjustment will be made for multiple testing but associated P-values will be interpreted cautiously.

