#### **9.2.5.2 Secondary immunogenicity measures**

The secondary immunogenicity measures are:

- a. To identify whether one or two doses of vaccine are required to satisfy the licensing criteria. We will assess whether either GSK or Baxter vaccine is able to meet all three CPMP criteria 21 days after the first vaccine dose. This will be assessed for each vaccine/age group, and each vaccine type;
- b. To examine the kinetics of the antibody responses to vaccination. This will be measured in terms of the ability of GSK or Baxter vaccine to meet any one, or all three, of the CPMP criteria 7 and 14 days after the first and second doses – for each vaccine/age group, and each vaccine type;
- c. To examine persistence of antibody at 6 months. This will be assessed in terms of the proportion of vaccinees who have inverse HI antibody titres of  $\geq 40$ , SRH areas of  $\geq 25\text{mm}^2$ , and inverse MN antibody titres of  $\geq 40$  and  $\geq 80$ . Antibody persistence will be assessed for each vaccine/age group, and each vaccine type;
- d. To evaluate the breadth of the antibody response to the antigenic variant (if appropriate, i.e., an antigenic drift variant emerges prior to the 2010-2011 influenza season). This will be done using the new antigenic variant as test antigen in HI, MN, and possibly by SRH tests by comparing the above primary immunogenicity measures on days 21 and 42 for each vaccine, by age group, and all age groups combined.

As with the primary immunogenicity outcomes comparisons will be made using parametric or non-parametric tests as appropriate for continuous outcomes, and Pearson's chi-square test or Fisher's exact test where appropriate for categorical outcomes. Further analyses using (generalised) linear models will explore the effect of baseline covariates on the outcomes. For populations (a) and (b), analyses using multiple imputation to allow for missing data will also be undertaken as a sensitivity analysis. No formal adjustment will be made for multiple testing but associated P-values will be interpreted cautiously.

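### Windows for the Day 28, 35 and 42 sera are counted from dose 1 although the endpoints are timed from dose 2, so evaluable sera can lie 3-11, 9-19 and 16-26 days after dose 2

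*Protocol*

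**What the plan says.** Section 1.2 fixes the origin of the day count: "The study day refers to the number of days after enrollment, with the day of first vaccination being designated day 0". The time and events table in section 6.1 carries the same origin over all eight visits, under the column heading "Days after the first vaccination".

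Section 9.1 then lists the study-day windows in which a serum is evaluable. The relevant ones are "Day 21 (window: Day 19–Day 23", "Day 28 (window; Day 26–Day 30", Day 32-38 for Day 35, and "Day 42 (window: Day 39–Day 45". Nothing in that section restarts the count at dose 2.

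The endpoints are timed from dose 2. Section 9.2.5.1 says: "The above immunogenicity criteria will be applied to sera collected 21 days after completion of vaccination, i.e., 21 days after the second vaccine dose". Section 9.2.5.2 assesses kinetics by the "CPMP criteria 7 and 14 days after the first and second doses".

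Dose 2 is given at the Day 21 visit. Section 6.1 and its table give that visit a tolerance of plus or minus 2 days. The procedure heading in section 8.1 reads "Visit 4: Day 21 (+2): Second vaccination", with a plus sign only. The per-protocol immunogenicity set in section 9.2.2(c) requires evaluable sera at the relevant time points.

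**The concern.** When a window is anchored on one event and the endpoint on a later event that has its own tolerance, the two tolerances add. A serum can pass section 9.1 and still be well off its target interval after dose 2. Another serum close to its target can fail.

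The kinetics objective is the most exposed. It applies the same criteria 7 and 14 days after each dose, as though the samples were like for like. After dose 1 the 7-day serum must fall at 6-8 days and the 14-day serum at 12-16 days. After dose 2 neither limit holds. For the primary time point, the interval analysed can differ by several days from the one defined in section 9.2.5.1. Any serum lost to the window also leaves the per-protocol set, in groups of 60 planned to leave at least 50.

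**Working it through.** **Inputs.** Windows come from section 9.1. The dose-2 visit is Day 19-23 (sections 6.1 and 9.1), or Day 21-23 if the section 8.1 heading is read literally. Targets are 7, 14 and 21 days after dose 2 (sections 9.2.5.1 and 9.2.5.2).

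**Step 1: reproduce the plan's windows.** Nominal study day plus or minus the visit tolerance gives 28 ± 2 = 26-30, 35 ± 3 = 32-38 and 42 ± 3 = 39-45. These match section 9.1 exactly and confirm that the anchor is dose 1.

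**Step 2: convert to days since dose 2.** Shortest interval = first day of window − latest dose-2 day. Longest interval = last day of window − earliest dose-2 day.

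| Serum | Target after dose 2 | Dose 2 on Day 19-23 | Dose 2 on Day 21-23 |
|---|---|---|---|
| Day 28 | 7 | 26−23 = 3 to 30−19 = 11 | 3 to 30−21 = 9 |
| Day 35 | 14 | 32−23 = 9 to 38−19 = 19 | 9 to 38−21 = 17 |
| Day 42 | 21 | 39−23 = 16 to 45−19 = 26 | 16 to 45−21 = 24 |

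In the first case, nominal 7-day and 14-day sera from different subjects overlap at 9-11 days, and Day 35 and Day 42 sera overlap at 16-19 days.

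**Step 3: are sera exactly on target rejected?** With dose 2 on Day 19-23, exact sera fall on Day 26-30 (19+7 to 23+7), Day 33-37 (19+14 to 23+14) and Day 40-44 (19+21 to 23+21). All are inside the windows, so none is rejected.

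**Step 4: sera near target.** Assume the same tolerances (±2, ±3, ±3 days) applied around dose 2. For Day 42 there are 5 dose-2 days × 7 intervals = 35 combinations within 21 ± 3. Six of them fall outside Day 39-45:
- dose 2 on Day 19, serum at 18 or 19 days (Day 37, 38);
- dose 2 on Day 20, serum at 18 days (Day 38);
- dose 2 on Day 22, serum at 24 days (Day 46);
- dose 2 on Day 23, serum at 23 or 24 days (Day 46, 47).

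The same count gives 6 of 35 for Day 35 and 6 of 5 × 5 = 25 for Day 28.

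**Step 5: accepted but off target.** For Day 42, the accepted pairs outside 18-24 days are dose 2 on Day 19 with serum on Day 44 or 45; Day 20 with 45; Day 22 with 39; and Day 23 with 39 or 40. That is 6 of 35. Day 35 also gives 6 of 35, and Day 28 gives 6 of 25. If dose-2 days and sample days were spread evenly and independently over their windows, these would be shares of 6/25 = 24% and 6/35 = 17%.

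**Range.** If every dose 2 were given on Day 21, the share would be zero. With dose 2 limited to Day 21-23 and even spread, it is 3/15 = 20% for Day 28 and 3/21 = 14% for Days 35 and 42.

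**The case against.** A reader might infer that correctly timed sera are thrown away. Step 3 shows otherwise: after an in-window dose 2, a serum exactly on target is always evaluable. It can be lost only if dose 2 itself is outside Day 19-23 (for the Day 28 serum) or Day 18-24 (for the other two). The precautions in section 7.3 do allow vaccination to be delayed, but such a subject may already fail the per-protocol rule on correct dosing.

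It is also tempting to say that the protocol breaches its own tolerance around dose 2. It states no such tolerance: ±2 and ±3 are given only around study days, and section 9.2.5.1 describes the licensing time point only as roughly three weeks. The shares in step 5 therefore rest on a borrowed tolerance. They also rest on an even spread that is probably unrealistic. The second diary card covers 7 days and is collected at the Day 28 visit, which is booked at the dose-2 visit; this should pull that visit towards 7 days after dose 2. Each extreme is one pair in 25 or 35, and 29 of 35 Day 42 pairs lie within ±3 days.

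The overlap of nominal 7-day and 14-day sera is between subjects only. Within one subject the Day 28 window closes on Day 30 and the Day 35 window opens on Day 32. The windows are the same for both vaccines, so they do not by themselves show a bias between vaccines. Section 9.2.5.1 does not name the per-protocol set as primary, and the full analysis set needs only one evaluable serum before and one after baseline.

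All of this stands and limits the harm. None of it removes the mismatch of anchors, which section 9.1 itself fixes and does not leave to a later analysis plan.

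**Conclusion.** The point holds as a defect in how section 9.1 and the visit schedule serve the protocol's own endpoints. Evaluable Day 28, 35 and 42 sera can lie 3-11, 9-19 and 16-26 days after dose 2, or 3-9, 9-17 and 16-24 days if dose 2 is limited to Day 21-23. These ranges follow from the stated windows alone.

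The shares of 24% and 17% are illustrations, probably towards the upper end. They need two assumptions: the study-day tolerances moved to dose 2, and an even spread of days. The protocol gives no frequencies of visit deviations and no figures for antibody rise by day, so the effect on the licensing criteria cannot be computed. For the primary time point it is probably small. The comparison of kinetics after dose 1 and after dose 2 is affected most, because the same label covers 6-8 days in one case and up to 3-11 days in the other. This should be corrected, but it does not threaten the primary conclusion.

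**What to change.** Count the Day 28, 35 and 42 blood-sampling windows from the actual date of dose 2, as 7 ± 2, 14 ± 3 and 21 ± 3 days. The accepted intervals then become 5-9, 11-17 and 18-24 days. Keep the Day 0 anchor for Days 7, 14 and 21. In the kinetics summaries, use actual days since dose 2.

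Make the change in section 9.1, in the design text and visit tables of the synopsis and section 6.1, and in the Visit 5-7 headings of section 8.1. At the same time, reconcile the plus-only tolerances in the Visit 4-7 headings with the plus-or-minus ones elsewhere. The difference may come from the conversion of the text from PDF, so check the source first. The change concerns sampling and evaluability only and leaves the timing of dose 2 as it is.

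The cost is wording. Section 7.7 already requires vaccination dates to be recorded, so no visit or sample is added. The schedule and the evaluability rule must change together: if visits are already booked by study day, re-anchoring section 9.1 alone would exclude some sera drawn on schedule.
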